6. END POINTS

6.1. Primary end point

The primary end point is defined as the **percentage of patients with at least one grade 3 or 4 adverse event (whether or not related to Sutent®)**, during the first 4 cycles of treatment (study follow-up period) according to the 'Common Terminology Criteria for Adverse Events' (CTCAE) version 4.03 of June 2010).

6.2. Secondary end points

- Dose reductions, interruptions and discontinuations of treatment (sunitinib)

Description of dose reductions:

- Proportion of patients with at least one dose reduction compared to the initial dose;
- Reasons for dose reductions;
- Changes in dose (initial dose or new prescribed dose).

Description of treatment interruptions:

- Proportion of patients who temporarily interrupt sunitinib;
- Mean duration of interruptions;
- Reasons for interruptions.

Permanent discontinuation of treatment

- Proportion of patients who discontinue Sunitinib permanently;
- Reasons for discontinuations.

- Unplanned medical procedures:

- Average number of unplanned consultations, whether or not related to sunitinib;
- Average number of unplanned hospitalizations, whether or not related to sunitinib.

- Treatment adherence

Adherence to treatment will be assessed from the **mean adherence score** and from the **proportion of "adherent" patients**. These criteria will be determined using the **Morisky scale (MMAS-4: 4-item Morisky Medication Adherence Scale)**, which consists of 4 items, together with a further question about adverse effects completed by the patient.

- Response to treatment

Response to treatment will be assessed from the **objective response rate (ORR)** according to RECIST criteria V1.1.

- **Patient and doctor satisfaction with the telephone call center**

Patient satisfaction with the call center will be assessed by:

- the **mean scores for each dimension on the satisfaction questionnaire**;
- the **proportion of patients/doctors who reported being “satisfied” or “very satisfied”** overall with the management by the telephone call center.

- **Description of telephone calls**

The telephone calls received during the study will be described by:

- the **number of completed calls** (planned and unplanned),
- the **actions taken** by the patient,
- the **actions taken** by the call center,
- the **actions taken** by the doctor,
- and the **declaration of adverse events**.

7. MANAGEMENT OF MISSING VALUES

The data from patients were recorded on an eCRF, except for the paper self-completed adherence and patient satisfaction questionnaires. Mandatory fields and consistency controls will be used to check data registered at the time. This strategy will be used to reduce missing data points or inconsistencies, particularly those concerning the major end points (AE, grades of AE and response to treatment etc.).

The analyses will be performed on the available data (“observed case analysis”), using the assumption that missing data are non-informative. The numbers of missing data points will be presented for each variable.

The response analysis will also be conducted on the FAS population by imputing missing responses as failure (= progression).

8. STATISTICAL METHODOLOGY AND STATISTICAL ANALYSES

The statistical analyses will be performed on SAS software (version 9.4 or subsequent, SAS Institute, North Carolina USA).

8.1. *Statistical methods*

8.1.1. **Descriptive analyses**

The analysis will be purely descriptive.

The descriptive analysis of qualitative variables will include numbers and frequency of each modality. The analysis of quantitative variables will include mean, standard deviation, values, median and extreme values. The number of missing values or values analyzed will be shown for each variable studied.

Consistency between two qualitative variables (assessment of adherence at W4 and W6 of cycles 1, 2 and 4) will be assessed using the Kappa coefficient [3] (cf. interpretation of the Kappa coefficient in annex 11.1).

8.1.2. **Analysis strategy**

In the principal analysis of the primary objective, all patients included in the “Call Center” arm will be analyzed in this group regardless of the number of calls received and all of their data will be used.

The analysis will be performed on an overall basis and according to the number of calls made by the call center as defined in section §5. Analysis population.

The statistical analyses and tabular models stipulated in this SAP will be used subject to sufficient numbers being available for the expanded analysis for a given variable.

8.2. Statistical analyses

8.2.1. Numbers

The **numbers of participating investigating doctors** will be described, together with the average number of patients included in the study. Participating and non-participating investigators will be described by geographical region (a variable derived from the post code of the investigator: cf. annex 1). The characteristics of active and non-active investigators will be described by geographical region, type of practice, urban or non-urban area and age and sex. The type of center facility will also be described (general hospital, university hospital, cancer center, etc.). These data will be obtained from an extraction from the database provided by Pfizer.

The **patient numbers** during the study will be displayed in a flow chart (cf. Figure 3 on page 35): patients reported, patients included, those followed up, those which leave the study and those who die.

Eligible patients who are not included into the study will be described from the data collected in the non-inclusion register in parallel with the same characteristics as patients who are included: age (derived from date of birth), sex and ECOG performance index. The reasons for non-inclusion will also be presented.

Follow-up of patients who are included will be described by:

- The median follow-up time in weeks: the time between the date of the inclusion visit and the date of the last follow-up consultation (If a patient stops treatment permanently during the follow-up period after the patient has stopped treatment will be included for patients in the CC arm).
- Average number of treatment cycles per patient;
- Average number of follow-up consultations achieved per patient;
- Average number completed calls per patient in the CC arm.

The major inclusion characteristics of patients who were followed up and those who were not followed up will be presented.

8.2.2. Description of the population when sunitinib treatment is started

Population analyzed: Included population

Analysis:

The patients will be described when they start treatment with sunitinib from all of the **inclusion data** collected:

- **Patients' sociodemographic characteristics:** Age (calculated as the time in years between date of birth and date of starting sunitinib), and sex;
- **Clinical Characteristics of the patients:** Risk score - Heng et al. criteria, Body Mass Index (BMI), ECOG performance index and Karnofsky index;
- **History of the disorder:** Time since the initial diagnosis of the primary renal cell carcinoma (calculated as the time in years between the date of initial diagnosis and the date of starting sunitinib), histology, stage of the disease, Fuhrman grade, treatment for the primary renal cell carcinoma (nephrectomy, radiotherapy or other), time since diagnosis of the 1st metastases (calculated as the time in years between the date of diagnosis of the 1st metastases and the date of starting sunitinib) and site of the metastases;
- **Past medical history:** Previous or ongoing comorbidities (diabetes, thyroid, etc.);
- **Hematologic and biochemical profile before starting sunitinib:** Time since the laboratory profile (in days), values of indices assessed (hemoglobin, platelets, LDH, etc.), abnormal values for other indices (hematocrit, leucocytes, etc.);
- **Other investigations performed:** Blood pressure, electrocardiogram (ECG), echocardiogram and previous orodental examination;
- **Concomitant symptomatic or preventative treatments:** Antiemetic or anti-diarrheal treatment, anti-neutropenic treatment, etc.;
- **Treatment supportive measures:** Person delivering the information on treatment, issuing of materials/support or document to the patient.

8.2.3. Description of patients during the follow-up period

Populations analyzed:

- Safety population: Call Center (all data) and standard follow-up (main data)

Analysis:

On an exploratory basis, before the analysis of the study objectives, the patients will be described from the data completed during the follow-up period by the investigating doctor:

- **Tumor assessment:** Radiologic investigation, response to treatment;
- **Clinical parameters:** ECOG, Karnofsky index and blood pressure;
- **Hematologic and biochemical profile:** Values of the indices measured (hemoglobin, calcium, etc.) and abnormal values for other indices (hematocrit, leucocytes, etc.);
- **Symptoms and tolerability:** Development of AEs: gastrointestinal or cardiac problems, etc.; Description serious AEs and non-serious AEs.
- **Concomitant, symptomatic or preventative treatments:** Prescription of another additional anti-tumor treatment, antiemetic treatment, anti-diarrheal treatment, etc.;
- **Planned and unplanned medical procedures:** number of calls, consultations and hospitalizations performed, specialty of the health professional in the event of calls or consultations, duration of hospitalization, reason for the medical procedure (AE or other) and actions implemented;
- **Measures to support treatment when treatment is continued:** Person delivering the information about treatment, issuing of materials/supports or documents to the patient.

The data listed above will be described for each follow-up time (end of cycle 1, 2 and 4).

8.2.4. Analysis of the primary end point

Analysis population: Safety population

The proportion of patients with at least one grade 3 or 4 AE whether or not related to sunitinib, will be estimated.

All of the grades 3 or 4 AEs defined by the 'Common Terminology Criteria for Adverse Events' (CTCAE v4.03 of June 2010), whether or not related to sunitinib, will be included when these occur during the study follow-up period (up to the end of the 4th treatment cycle or until the treatment is stopped if it is discontinued in the 1st, 2nd or 3rd cycle). All of the AEs will be included whether these are declared by the doctor or by the nurse.

The analyses will be performed both on an overall basis and according to the number of calls made by the call center.

Sensitivity analyses:

The sensitivity analyses will be performed:

- Sensitivity to duration of patient treatment: the results will also be expressed as standardized grade 3 or 4 AE rates developed by the patient and reported over the 6 months of treatment. These rates will be defined by each patient as the number of events which occurred/number of treatment months with sunitinib/ 6).

Secondary analysis:

- **The incidence of the main grade 3 or 4 AEs, whether or not related to sunitinib,** will also be presented in these patients according to the MedDRA SOC (System Organ Class) and PT (Preferred Term) classification. Only categories involving at least 2% of patients will be presented.

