8.7.1. Analysis strategy

The main analysis will be performed on the population of patients treated with sunitinib, taking into account all grade 3 or 4 AEs observed. Sensitivity analyses will be conducted:

- **using the "missing=failure" strategy**

Any missing values will be replaced by the value corresponding to failure, i.e. grade 3 or 4 AE. For the main outcome measure analysis, this implies that the patient shall be considered as being in a situation of failure.

- **on a population of treated patients compliant with the procedure**

The choice of a compliance threshold upon intervention must be defined in the detailed statistical analysis plan and before the final analysis is performed. This threshold shall consist in a minimum number of successful calls out of the theoretical total number of 14 calls over the entire follow-up period.

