8.7.4. Study report

The results will be presented in a study report. This study report will accurately and exhaustively summarise the study objectives, methods, results and their interpretation. It shall be reviewed and validated by the scientific committee. Any changes made to the statistical methods must be reported and documented in the clinical/statistical report.

A summary version of the final report will be sent to each participating physician after validation of results by the Scientific Committee.

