9.2. Patient withdrawal from the study

A patient can withdraw from the study at any time, or be removed at any time by decision of the participating physician.

If a patient fails to attend a scheduled visit, all efforts must be made to contact this patient. In all cases, withdrawal from the study must be documented. The participating physician must specify the reasons for withdrawal from the study, he/she must attempt to make a further appointment for a visit and, if necessary, to monitor any unresolved adverse event.

If the patient withdraws from the study, also withdrawing his/her consent to the disclosure of future information, no other evaluations should be conducted and no additional data should be collected.

The sponsor may keep the data collected prior to withdrawal of consent.

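### SAP section 8.2.4 omits, without a reason, the missing=failure sensitivity analysis of the primary proportion that protocol section 8.7.1 commits to

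*SAP*

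**What the plan says.** Protocol section 8.7.1 says that sensitivity analyses will accompany the main analysis and names two. The first is missing=failure: "Any missing values will be replaced by the value corresponding to failure, i.e. grade 3 or 4 AE". It is tied explicitly to the primary endpoint: "For the main outcome measure analysis, this implies that the patient shall be considered as being in a situation of failure". The second restricts the analysis to treated patients who complied with the call procedure.

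SAP section 8.2.4 keeps the second as a breakdown by number of calls, using the threshold in SAP section 5.2. Under its sensitivity analyses it then lists a single item: "Sensitivity to duration of patient treatment: the results will also be expressed as standardized grade 3 or 4 AE rates". The Table 30 shell has Yes and No rows with an interval for Yes, the number of events per patient, and the standardised rate. It has no missing=failure row and no row for missing values, although Tables 40 and 44 do have a missing-value row.

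SAP section 7 sets an observed-case analysis, "using the assumption that missing data are non-informative". It keeps failure imputation only for tumour response, "by imputing missing responses as failure (= progression", and section 8.2.5.4 repeats this. The SAP introduction says the document is based on protocol amendment 3.1, which is the version containing the commitment. The SAP gives no reason for leaving the analysis out.

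**The concern.** The proportion with a grade 3 or 4 event is the headline result. SAP section 4.1 plans no tests, and SAP section 3 allows the results to be discussed against the SANTORIN cohort, for which protocol section 6.1.2 gives 58%. Missing=failure is the protocol's own check on the assumption made in SAP section 7, and it can only move the proportion upward. Imputing failure was not rejected in principle, because it survives for a secondary endpoint.

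The documents expect some incomplete follow-up. SAP section 8.2.1 and Table 9 describe patients who were not followed up. Such a patient, if treated, belongs to the Safety population, but the SAP does not say whether that patient is left out of the proportion or counted as No. After withdrawal of consent to further disclosure, protocol section 9.2 says "no other evaluations should be conducted and no additional data should be collected", so a patient who withdraws while still taking sunitinib has unobserved time inside the event window. An event that never receives a grade from nurse or physician cannot be classified. Neither document defines a missing primary outcome.

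**Working it through.** **1. The plan's own figure.** Protocol section 8.5 uses i = 1.96 × √(p(1−p)/n). With p = 0.50 and n = 100, i = 1.96 × √(0.25/100) = 0.098, so the stated ±9.8 points reproduces. The omission itself is a matter of text and does not depend on this figure.

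**2. Does the listed sensitivity analysis do the same job?** The intended standardised rate is events / (treatment months / 6).
- One event in 3 months: 1 / (3/6) = 2.0 per 6 months.
- No events: 0, whatever the duration.

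The rate rescales recorded events by exposure. A patient with no recorded event scores 0 whether or not the data are complete, so unknown outcomes are not tested. As printed, the formula has a closing bracket without an opening one. Read left to right, the same patient would score 1/3/6 = 0.056.

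**3. Size of the omitted check.** Inputs:
- n = 100 (protocol section 8.5);
- p, the event proportion among patients with a known outcome: 50% (the planning value in section 8.5) or 58% (the SANTORIN figure in section 6.1.2, as illustration only);
- u, the number of patients with a missing outcome. This is an **assumption**, because the documents give no missing rate.

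Observed-case result = p, on n − u patients. Missing=failure result = [p(n − u) + u] / n. Shift = (u/n)(1 − p).

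| u (assumed) | p = 58%: missing=failure | shift (points) | p = 50%: missing=failure | shift (points) |
|---|---|---|---|---|
| 0 | 58.0% | 0 | 50.0% | 0 |
| 2 | 58.8% | 0.8 | 51.0% | 1.0 |
| 5 | 60.1% | 2.1 | 52.5% | 2.5 |
| 10 | 62.2% | 4.2 | 55.0% | 5.0 |
| 20 | 66.4% | 8.4 | 60.0% | 10.0 |

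Example: p = 0.58, u = 10 gives (0.58 × 90 + 10)/100 = 62.2/100.

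**4. Against the planned precision.** For the shift to equal 9.8 points, u/n must be 0.098/(1 − p). That is 19.6% missing at p = 50% and 23.3% at p = 58%. With 2 to 5 missing patients the shift stays well inside the interval.

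The formula reads the observed-case rule literally: patients classed as missing leave the denominator of the main figure. The SAP does not say so for this endpoint.

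**The case against.** The strongest reply is that little is likely to be missing. SAP section 7 relies on mandatory fields and consistency checks aimed at adverse events and their grades. It promises missing counts for each variable, and Table 9 compares patients who were and were not followed up. SAP section 8.2.4 counts events declared by the doctor or the nurse, and protocol section 7.3.1 lets the nurse propose a grade, so an event awaiting the physician's grade is not automatically lost. Protocol section 9.2 lets the sponsor keep data collected before consent is withdrawn. All of this stands. It makes a small shift more likely, and it supports observed cases as the main analysis. It does not explain dropping the analysis that tests the assumption, and no field check can recover on-treatment time after a patient has withdrawn.

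Three stronger readings are tempting, and the documents do not support them.
- A reader might infer that patients who stop for toxicity, progression or death are missing. SAP section 8.2.4 closes the event window when treatment stops, and the end-of-treatment form in protocol Appendix 6 asks for an event report when the reason is toxicity or death. Their outcome is defined.
- A reader might therefore recode every event-free early leaver as a failure and call the result an upper bound. Protocol section 8.7.1 replaces missing values only. That recoding would be a new analysis.
- A reader might infer that the SAP breaches protocol section 8.7.4. That section says "Any changes made to the statistical methods must be reported and documented in the clinical/statistical report". It governs the report, which is not among the documents, so no breach is shown.

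**Conclusion.** The mismatch is real: the protocol commits to missing=failure for the primary endpoint, and the SAP omits it without a reason while assuming non-informative missingness. The duration-standardised rate is no substitute.

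The consequence is bounded by (share missing) × (1 − observed rate). With 100 patients and 58% observed, that is 0.8 to 8.4 points for 2 to 20 missing patients. These counts are assumptions, and nothing in the documents supports any particular one. With none missing, the check confirms the result. Severity is minor to moderate: the study is descriptive and the gap may be small, but the affected figure is the headline one. The bracket in the rate formula is a typographical slip and adds no weight.

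**What to change.** In SAP section 8.2.4 and Table 30:
1. Restore the missing=failure proportion with its 95% CI, labelled as a sensitivity result.
2. Define missing as treated Call Center patients with no recorded grade 3 or 4 event whose adverse event or grade data are absent for part of the on-treatment window. Examples are withdrawal of consent or loss to follow-up while on sunitinib, no follow-up visit, or an event with no grade from nurse or physician. Say how these patients enter the main figure.
3. Show the number of such patients in Table 30.
4. State that patients whose window closed at treatment stop without an event count as No and are not recoded.
5. Correct the standardised rate to events / (treatment months / 6).

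If the analysis is not restored, the minimum is a sentence in the SAP saying that it was removed and why.

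The cost is a few sentences and a few table rows, from data already planned for the e-CRF and the call-centre system. The downside is that a less favourable figure will stand beside the headline and must not be read as the estimate.
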